Liver Failure	Digestive	740	1,480	2,220	2,960	3,700
Anorectal Prolapse	Digestive	680	1,360	2,040	2,720	3,400
Cholangitis	Digestive	650	1,300	1,950	2,600	3,250
Anorectal Fistula	Digestive	610	1,220	1,830	2,440	3,050
Coeliac Disease	Digestive	600	1,200	1,800	2,400	3,000

Portal Hypertension	Digestive	590	1,180	1,770	2,360	2,950
Oesophageal Varices	Digestive	560	1,120	1,680	2,240	2,800
Crohns Disease	Digestive	530	1,060	1,590	2,120	2,650
Volvulus	Digestive	410	820	1,230	1,640	2,050
Angiodysplasia of colon	Digestive	350	700	1,050	1,400	1,750
Autoimmune liver disease	Digestive	150	300	450	600	750
Deafness	Ear	15,010	30,020	45,030	60,040	75,050
Tinnitus	Ear	6,190	12,380	18,570	24,760	30,950
Meniere's Disease	Ear	470	940	1,410	1,880	2,350
Raised Total Cholesterol	Endocrine	36,530	73,060	109,590	146,120	182,650
Raised LDL-C	Endocrine	24,180	48,360	72,540	96,720	120,900
Obesity	Endocrine	16,180	32,360	48,540	64,720	80,900
Type 2 Diabetes Mellitus	Endocrine	13,940	27,880	41,820	55,760	69,700
Raised Triglycerides	Endocrine	13,780	27,560	41,340	55,120	68,900
Low HDL-C	Endocrine	9,740	19,480	29,220	38,960	48,700
Thyroid Disease	Endocrine	7,730	15,460	23,190	30,920	38,650
Diabetes Mellitus – other or not specified	Endocrine	1,030	2,060	3,090	4,120	5,150
Hyperparathyroidism	Endocrine	670	1,340	2,010	2,680	3,350
Polycystic Ovarian Syndrome	Endocrine	370	740	1,110	1,480	1,850
Syndrome of Inappropriate AntiDiuretic Hormone	Endocrine	210	420	630	840	1,050
Type 1 Diabetes Mellitus	Endocrine	100	200	300	400	500
Cataract	Eye	20,500	41,000	61,500	82,000	102,500
Diabetic Eye Disease	Eye	5,700	11,400	17,100	22,800	28,500
Glaucoma	Eye	3,640	7,280	10,920	14,560	18,200
Macular Degeneration	Eye	3,610	7,220	10,830	14,440	18,050
Blindness	Eye	2,030	4,060	6,090	8,120	10,150
Retinal Detachment	Eye	1,080	2,160	3,240	4,320	5,400
Retinal Vascular Occlusion	Eye	940	1,880	2,820	3,760	4,700
Anterior Uveitis	Eye	850	1,700	2,550	3,400	4,250
Ptosis	Eye	810	1,620	2,430	3,240	4,050
Keratitis	Eye	730	1,460	2,190	2,920	3,650

Scleritis	Eye	590	1,180	1,770	2,360	2,950
Erectile Dysfunction	Genitourinary	23,340	46,680	70,020	93,360	116,700
Benign Prostatic Hyperplasia	Genitourinary	9,645	19,290	28,935	38,580	48,225
Acute Kidney Injury	Genitourinary	9,100	18,200	27,300	36,400	45,500
Chronic Kidney Disease	Genitourinary	8,350	16,700	25,050	33,400	41,750
Menorrhagia	Genitourinary	7,780	15,560	23,340	31,120	38,900
Urinary Incontinence	Genitourinary	7,780	15,560	23,340	31,120	38,900

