Answer this question for blood relations only. If you are not sure if your father suffered from any of the listed illnesses, please select 'Do not know'. If you know your father suffered from certain listed illnesses but are unsure about others, only select the ones you are sure about.

[AUTO_A_DAD]

Has your father ever been diagnosed with any of the following autoimmune disorders?

- 0 Rheumatoid arthritis
- 1 Lupus
- 2 Inflammatory Bowel Disease (IBD)
- 3 Multiple Sclerosis (MS)
- 4 Graves' disease
- 5 Guillain-Barre syndrome
- 6 Psoriasis
- 7 Other (not listed)
- 1 I don't know
- 3 Prefer not to answer

[BLOOD_A_DAD]

Has your father ever been diagnosed with any of the following types of anaemia?

- 0 Iron deficiency anaemia
- 1 Vitamin deficiency anaemia

- 2 Sickle cell anaemia
- 3 Aplastic anaemia
- 4 Thalassemia
- 5 Other (not listed)
- 1 I don't know
- 3 Prefer not to answer

[CANC_A_DAD (CONNECT)]

Which type(s) of cancer specifically was your father diagnosed with?
Please indicate where the cancer originated, even if it spread to other body areas

- 0 Anal
- 1 Bladder
- 2 Brain
- 3 Breast
- 4 Cervical
- 5 Colon/rectal
- 6 Oesophageal
- 7 Head and neck (Including cancers of the mouth, sinuses, nose, or throat. Not including brain or skin cancers.)
- 8 Gastric
- 9 Kidney
- 10 Leukaemia (blood and bone marrow)
- 11 Liver
- 12 Lung or bronchial
- 14 Lymphoma
- 15 Ovarian
- 16 Pancreatic
- 17 Prostate
- 18 Skin. -> GO TO DAD_CANC_B
- 19 Stomach
- 20 Testicular
- 21 Thyroid
- 22 Uterine (endometrial)
- 23 Another type of cancer
- 24 I know they had cancer, but don't know what type
- 1 I don't know
- 3 Prefer not to answer

[CANC_B_DAD (CONNECT)]

What type of skin cancer specifically was your father diagnosed with?

- 0 Melanoma
- 1 Basal cell

- 2 Squamous cell
- 1 I don't know
- 3 Prefer not to answer

[DIG_A_DAD (CONNECT)]

Has your father ever been diagnosed with any of the following digestive system problems?

- 0 Gastro-oesophageal Acid Reflux (GORD)
- 1 Barrett's Oesophagus
- 2 Irritable bowel syndrome
- 3 Inflammatory Bowel Disease
- 4 Diverticulitis or Diverticulosis
- 5 Ulcerative Colitis
- 6 Crohn's Disease
- 7 Coeliac Disease (also known as Gluten-Sensitive Enteropathy)
- 8 Gallstones (Biliary Stones)
- 9 Fatty liver disease
- 10 Liver Cirrhosis
- 11 Hepatitis
- 12 Pancreatitis
- 5 Other (not listed)
- 1 I don't know
- 3 Prefer not to answer

[EN_A_DAD]

Has your father ever been diagnosed with the following conditions?

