- 0 Type 1 diabetes
- 1 Type 2 diabetes
- 2 overactive thyroid
- 3 underactive thyroid
- 4 Cushing syndrome
- 5 Lactose intolerance
- 6 Vitamin A deficiency
- 7 Thiamine deficiency
- 8 Vitamin D deficiency
- 3 Other (not listed)
- 1 I don't know
- 3 Prefer not to answer

[EYE_A_DAD]

Has your father ever been diagnosed with any of the following eye or visual problems?

- 0 Glaucoma
- 1 Visual impairment including blindness
- 2 Double vision
- 3 Night blindness
- 4 Colour blindness
- 5 Macular degeneration
- 6 Cataracts
- 7 Retinal detachment
- 8 Diabetic retinopathy
- 9 Other (not listed)
- 1 I don't know
- 3 Prefer not to answer

[FRAC_A_DAD]

What type of fractures, breaks, joint or bone problems have your father experienced?

- 0 Hip fracture
- 1 Osteoporosis
- 2 Osteoarthritis (arthritis)
- 3 Gout
- 4 Other (not listed)
- 1 I don't know
- 3 Prefer not to answer

[HEART_A_DAD (CONNECT)]

Has your father ever been diagnosed with any of the following heart or circulatory diseases?

- 0 B-12 Deficiency (Pernicious Anaemia)
- 1 Coronary Artery/Coronary Heart Disease
- 2 Congestive Heart Failure
- 3 High Cholesterol
- 4 Heart Attack (Myocardial Infarction)
- 5 Abnormal Heart Rhythm (Arrhythmia)
- 6 Chest Pain (Angina)
- 7 Heart Valve Problems
- 8 High Blood Pressure (Hypertension) [Please do **not** include hypertension during pregnancy.]
- 9 Blood Clots (Deep Vein Thrombosis, Pulmonary Embolism)
- 10 Stroke
- 11 Other (not listed)
- 1 I don't know
- 3 Prefer not to answer

[KIDN_A_DAD (CONNECT)]

Has your father ever been diagnosed with any of the following kidney or urinary tract problems?

- 0 Kidney stones
- 1 Chronic kidney disease (or chronic kidney failure)
- 2 Other (not listed)
- 1 I don't know
- 3 Prefer not to answer

[LUNG_A_DAD (CONNECT)]

Has your father ever been diagnosed with any of the following lung or respiratory conditions?

- 0 Chronic Obstructive pulmonary disease, COPD (including emphysema and chronic bronchitis)
- 1 Lung fibrosis
- 2 Bronchiectasis
- 3 Asthma
- 4 Hay Fever (Allergic to pollen or Allergic Rhinitis)
- 5 Other (not listed)
- 1 I don't know
- 3 Prefer not to answer

[ND_A_DAD]

Has your father ever been diagnosed with one or more of the following conditions by a professional, even if your father don't have it currently?

Please include disorders even if your father did not need treatment for them or if your father did not agree with the diagnosis. Select ALL that apply

- 0 Autism spectrum disorder

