- 2 Enlarged prostate
- 3 Fibrocystic Breast, or another Benign Breast Disease (such as proliferative Benign Breast Disease or LCIS)
- 4 Ductal Carcinoma in situ (DCIS)
- 5 Uterine Fibroids
- 6 Other (not listed)

- 1 I don't know
- 3 Prefer not to answer

[Y16 (UKB)]

Is your biological mother still alive?

SELECT one of 4 from

- 1 Yes
- 0 No -> GO TO Y16B (UKB)
- 1 Do not know -> GO TO Y16D (UKB)
- 3 Prefer not to answer -> GO TO Y16D (UKB)

[Y16A (UKB)]

What is her age now?

Enter INTEGER

[Require > current age, ≤ 122

Units: years]

OR

- 1 Do not know

OR

- 3 Prefer not to answer

[Y16B (UKB)]

What was her age when she died?

Enter INTEGER

[Require > current age, ≤ 122

Units: years]

OR

- 1 Do not know

OR

- 3 Prefer not to answer

[Y16D (UKB)]

Has/did your mother ever suffer from? (You can select more than one answer)

TOGGLE

[Require ≥1 choices]

- 2 Autoimmune disorder -> GO TO AUTO_A
- 3 Blood disorders (Anaemia) -> GO TO BLOOD_A
- 2 Cancer -> GO TO CANC_A
- 3 Complications or difficulties in pregnancy or childbirth -> GO TO PREG_A
- 4 Digestive system or liver problems -> GO TO DIG_A

- 5 Endocrine, nutritional and metabolic disorders (e.g., diabetes, thyroid disorder, vitamin deficiencies) -> **GO TO EN_A**
- 6 Eye or visual problems -> **GO TO EYE_A**
- 7 Fractures, breaks, or joint problems -> **GO TO FRAC_A**
- 8 Heart or circulatory disease (e.g. high blood pressure or stroke) -> **GO TO HEART_A**
- 9 Kidney or urinary system disorders -> **GO TO KIDN_A**
- 10 Lung or respiratory problems -> **GO TO LUNG_A**
- 11 Mental health conditions (e.g.depression, bipolar disorder) -> **GO TO MH_A**
- 12 Neurodevelopmental conditions (e.g., Autism spectrum disorder, ADHD) -> **GO TO ND_A**
- 13 Neurological disorders (things that affect that brain or nervous system) -> **GO TO NEU_A**
- 14 Reproductive system problems -> **GO TO REPRO_A**
- 15 Other not listed -> **GO TO Y17 (UKB)]**
- 16 None of these -> **GO TO Y17 (UKB)]**
- 1 I don't know [**EXCLUSIVE**] -> **GO TO Y17 (UKB)]**
- 3 Prefer not to answer [**EXCLUSIVE**] -> **GO TO Y17 (UKB)]**

Answer this question for blood relations only. If you are not sure if your mother suffered from any of the listed illnesses, please select 'Do not know'. If you know your mother suffered from certain listed illnesses but are unsure about others, only select the ones you are sure about.

[AUTO_A_MOM]

Has your mother ever been diagnosed with any of the following autoimmune disorders?

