- 0 Rheumatoid arthritis
- 1 Lupus
- 2 Inflammatory Bowel Disease (IBD)
- 3 Multiple Sclerosis (MS)
- 4 Graves' disease
- 5 Guillain-Barre syndrome
- 6 Psoriasis
- 7 Other (not listed)
- 1 I don't know
- 3 Prefer not to answer

[BLOOD_A_MOM]

Has your mother ever been diagnosed with any of the following types of anaemia?

- 0 Iron deficiency anaemia
- 1 Vitamin deficiency anaemia
- 2 Sickle cell anaemia
- 3 Aplastic anaemia

- 4 Thalassaemia
- 5 Other (not listed)
- 1 I don't know
- 3 Prefer not to answer

[CANC_A_MOM (CONNECT)]

Which type(s) of cancer specifically was your mother diagnosed with?
Please indicate where the cancer originated, even if it spread to other body areas

- 0 Anal
- 1 Bladder
- 2 Brain
- 3 Breast
- 4 Cervical
- 5 Colon/rectal
- 6 Oesophageal
- 7 Head and neck (Including cancers of the mouth, sinuses, nose, or throat. Not including brain or skin cancers.)
- 8 Gastric
- 9 Kidney
- 10 Leukaemia (blood and bone marrow)
- 11 Liver
- 12 Lung or bronchial
- 14 Lymphoma
- 15 Ovarian
- 16 Pancreatic
- 17 Prostate
- 18 Skin
- 19 Stomach
- 20 Testicular
- 21 Thyroid
- 22 Uterine (endometrial)
- 23 Another type of cancer
- 24 I know they had cancer, but don't know what type
- 1 I don't know
- 3 Prefer not to answer

[CANC_B_MOM (CONNECT)]

What type of skin cancer specifically was your mother diagnosed with?

- 3 Melanoma
- 4 Basal cell
- 5 Squamous cell
- 1 I don't know

-3 Prefer not to answer

[PREG_A_MOM (CONNECT+ICD)]

What type of complication or difficulties with pregnancy or childbirth has your mother experienced?

- 0 Miscarriage (pregnancy loss before 20 weeks)
- 1 Stillbirth (pregnancy loss after 20 weeks)
- 2 Live birth and still birth (loss of one or more multiples)
- 3 Ectopic or tubal pregnancy
- 4 Trying to get pregnant for more than a year but not getting pregnant during that time
- 5 hyperemesis gravidarum
- 6 Gestational diabetes
- 7 Preterm labour and delivery
- 8 Complicated labour and delivery
- 9 Traumatic labour or delivery
- 10 Pre-eclampsia
- 11 Eclampsia
- 12 Gestational hypertension
- 13 Other (not listed)
- 1 I don't know
- 3 Prefer not to answer

[DIG_A_MOM (CONNECT)]

Has your mother ever been diagnosed with any of the following digestive system problems?

- 0 Gastro-oesophageal Acid Reflux (GORD)
- 1 Barrett's Oesophagus
- 2 Irritable bowel syndrome
- 3 Inflammatory Bowel Disease
- 4 Diverticulitis or Diverticulosis
- 5 Ulcerative Colitis
- 6 Crohn's Disease

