- 7 Coeliac Disease (also known as Gluten-Sensitive Enteropathy)
- 8 Gallstones (Biliary Stones)
- 9 Fatty liver disease
- 10 Liver Cirrhosis
- 11 Hepatitis
- 12 Pancreatitis
- 5 Other (not listed)
- 1 I don't know
- 3 Prefer not to answer

[EN_A_MOM]

Has your mother ever been diagnosed with the following conditions?

- 0 Type 1 diabetes
- 1 Type 2 diabetes
- 2 overactive thyroid
- 3 underactive thyroid
- 4 Cushing syndrome
- 5 Lactose intolerance
- 6 Vitamin A deficiency
- 7 Thiamine deficiency
- 8 Vitamin D deficiency
- 3 Other (not listed)
- 1 I don't know
- 3 Prefer not to answer

[EYE_A_MOM]

Has your mother ever been diagnosed with any of the following eye or visual problems?

- 1 Glaucoma
- 1 Visual impairment including blindness
- 2 Double vision
- 3 Night blindness
- 4 Colour blindness
- 5 Macular degeneration
- 6 Cataracts
- 7 Retinal detachment
- 8 Diabetic retinopathy
- 9 Other (not listed)
- 1 I don't know
- 3 Prefer not to answer

[FRAC_A_MOM]

What type of fractures, breaks, joint or bone problems have your mother experienced?

- 15 Hip fracture
- 1 Osteoporosis
- 2 Osteoarthritis (arthritis)
- 3 Gout
- 4 Other (not listed)
- 1 I don't know
- 3 Prefer not to answer

[HEART_A_MOM (CONNECT)]

Has your mother ever been diagnosed with any of the following heart or circulatory diseases?

- 0 B-12 Deficiency (Pernicious Anaemia)
- 1 Coronary Artery/Coronary Heart Disease
- 2 Congestive Heart Failure
- 3 High Cholesterol
- 4 Heart Attack (Myocardial Infarction)
- 5 Abnormal Heart Rhythm (Arrhythmia)
- 6 Chest Pain (Angina)
- 7 Heart Valve Problems
- 8 High Blood Pressure (Hypertension) [Please do **not** include hypertension during pregnancy.]
- 9 Blood Clots (Deep Vein Thrombosis, Pulmonary Embolism)
- 10 Stroke
- 11 Other (not listed)
- 1 I don't know
- 3 Prefer not to answer

[KIDN_A_MOM (CONNECT)]

Has your mother ever been diagnosed with any of the following kidney or urinary tract problems?

- 0 Kidney stones
- 1 Chronic kidney disease (or chronic kidney failure)
- 2 Other (not listed)
- 1 I don't know
- 3 Prefer not to answer

[LUNG_A_MOM (CONNECT)]

Has your mother ever been diagnosed with any of the following lung or respiratory conditions?

- 0 Chronic Obstructive pulmonary disease, COPD (including emphysema and chronic bronchitis)
- 1 Lung fibrosis
- 2 Bronchiectasis
- 3 Asthma
- 4 Hay Fever (Allergic to pollen or Allergic Rhinitis)
- 5 Other (not listed)
- 1 I don't know

-3 Prefer not to answer

[ND_A_MOM]

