- 1 Stillbirth (pregnancy loss after 20 weeks)
- 2 Live birth and still birth (loss of one or more multiples)
- 3 Ectopic or tubal pregnancy
- 4 Trying to get pregnant for more than a year but not getting pregnant during that time
- 5 hyperemesis gravidarum
- 6 Gestational diabetes
- 7 Preterm labour and delivery
- 8 Complicated labour and delivery
- 9 Traumatic labour or delivery
- 10 Pre-eclampsia
- 11 Eclampsia
- 12 Gestational hypertension

- 13 Other (not listed)
- 1 I don't know
- 3 Prefer not to answer

[DIG_A_SIB (CONNECT)]

Has your brother or sister ever been diagnosed with any of the following digestive system problems?

- 0 Gastro-oesophageal Acid Reflux (GORD)
- 1 Barrett's Oesophagus
- 2 Irritable bowel syndrome
- 3 Inflammatory Bowel Disease
- 4 Diverticulitis or Diverticulosis
- 5 Ulcerative Colitis
- 6 Crohn's Disease
- 7 Coeliac Disease (also known as Gluten-Sensitive Enteropathy)
- 8 Gallstones (Biliary Stones)
- 9 Fatty liver disease
- 10 Liver Cirrhosis
- 11 Hepatitis
- 12 Pancreatitis
- 5 Other (not listed)
- 1 I don't know
- 3 Prefer not to answer

[EN_A_SIB]

Has your brother or sister ever been diagnosed with the following conditions?

- 0 Type 1 diabetes
- 1 Type 2 diabetes
- 2 overactive thyroid
- 3 underactive thyroid
- 4 Cushing syndrome
- 5 Lactose intolerance
- 6 Vitamin A deficiency
- 7 Thiamine deficiency
- 8 Vitamin D deficiency
- 3 Other (not listed)
- 1 I don't know
- 3 Prefer not to answer

[EYE_A_SIB]

Has your brother or sister ever been diagnosed with any of the following eye or visual problems?

- 2 Glaucoma
- 1 Visual impairment including blindness
- 2 Double vision
- 3 Night blindness
- 4 Colour blindness
- 5 Macular degeneration
- 6 Cataracts
- 7 Retinal detachment
- 8 Diabetic retinopathy
- 9 Other (not listed)
- 1 I don't know
- 3 Prefer not to answer

[FRAC_A_SIB]

What type of fractures, breaks, joint or bone problems have your brother or sister experienced?

- 30 Hip fracture
- 1 Osteoporosis
- 2 Osteoarthritis (arthritis)
- 3 Gout
- 4 Other (not listed)
- 1 I don't know
- 3 Prefer not to answer

[HEART_A_SIB (CONNECT)]

Has your brother or sister ever been diagnosed with any of the following heart or circulatory diseases?

- 0 B-12 Deficiency (Pernicious Anaemia)
- 1 Coronary Artery/Coronary Heart Disease
- 2 Congestive Heart Failure
- 3 High Cholesterol
- 4 Heart Attack (Myocardial Infarction)
- 5 Abnormal Heart Rhythm (Arrhythmia)
- 6 Chest Pain (Angina)
- 7 Heart Valve Problems

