What type of complication or difficulties with pregnancy or childbirth have you experienced?

- 0 Miscarriage (pregnancy loss before 20 weeks)
- 1 Stillbirth (pregnancy loss after 20 weeks)
- 2 Live birth and still birth (loss of one or more multiples)
- 3 Ectopic or tubal pregnancy
- 4 Trying to get pregnant for more than a year but not getting pregnant during that time
- 5 hyperemesis gravidarum
- 6 Gestational diabetes
- 7 Preterm labour and delivery
- 8 Complicated labour and delivery
- 9 Traumatic labour or delivery
- 10 Pre-eclampsia

- 11 Eclampsia
- 12 Gestational hypertension
- 13 Other (not listed)
- 1 I don't know
- 3 Prefer not to answer

[DIG_A (CONNECT)]

Have you ever been diagnosed with any of the following digestive system problems by a doctor or other health professional?

- 0 Gastro-oesophageal Acid Reflux (GORD)
- 1 Barrett's Oesophagus
- 2 Irritable bowel syndrome
- 3 Inflammatory Bowel Disease
- 4 Diverticulitis or Diverticulosis
- 5 Ulcerative Colitis
- 6 Crohn's Disease
- 7 Coeliac Disease (also known as Gluten-Sensitive Enteropathy)
- 8 Gallstones (Biliary Stones)
- 9 Fatty liver disease
- 10 Liver Cirrhosis
- 11 Hepatitis
- 12 Pancreatitis
- 5 Other (not listed)
- 1 I don't know
- 3 Prefer not to answer

[EN_A]

Have you ever been diagnosed with the following conditions by a doctor or health professional?

- 0 Type 1 diabetes
- 1 Type 2 diabetes
- 2 overactive thyroid
- 3 underactive thyroid
- 4 Cushing syndrome
- 5 Lactose intolerance
- 6 Vitamin A deficiency
- 7 Thiamine deficiency
- 8 Vitamin D deficiency
- 3 Other (not listed)
- 1 I don't know
- 3 Prefer not to answer

[EYE_A]

Have you ever been diagnosed with any of the following eye or visual problems by a doctor or other health professional?

- 3 Glaucoma
- 1 Visual impairment including blindness
- 2 Double vision
- 3 Night blindness
- 4 Colour blindness
- 5 Macular degeneration
- 6 Cataracts
- 7 Retinal detachment
- 8 Diabetic retinopathy
- 9 Other (not listed)
- 1 I don't know
- 3 Prefer not to answer

[FRAC_A]

What type of fractures, breaks, joint or bone problems have you experienced?

- 45 Hip fracture
- 1 Osteoporosis
- 2 Osteoarthritis (arthritis)
- 3 Gout
- 4 Other (not listed)
- 1 I don't know
- 3 Prefer not to answer

[HEART_A (CONNECT)]

Have you ever been diagnosed with any of the following heart or circulatory diseases by a doctor or other health professional?

- 0 B-12 Deficiency (Pernicious Anaemia)
- 1 Coronary Artery/Coronary Heart Disease

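### The relatives' diabetes lists have no answer for a participant who knows a parent or sibling had diabetes but not which type

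*Protocol*

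**What the plan says.** In Appendix E, Section 4 (family health history), a gate question for each relative (Y13D father, Y16D mother, Y19 siblings) lists broad disease groups. One group reads "Endocrine, nutritional and metabolic disorders (e.g., diabetes, thyroid disorder, vitamin deficiencies", and ticking it leads to a detailed list.

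- EN_A_DAD: "Has your father ever been diagnosed with the following conditions"
- EN_A_MOM: "Has your mother ever been diagnosed with the following conditions"
- EN_A_SIB: "Has your brother or sister ever been diagnosed with the following conditions"

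Each list contains Type 1 diabetes, "Type 2 diabetes", over- and underactive thyroid, Cushing syndrome, lactose intolerance, three vitamin deficiencies, an unlisted-other option, a do-not-know option and a refusal. The participant's own list in Section 5 (EN_A, "Have you ever been diagnosed with the following conditions by a doctor or health professional") has the same options.

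The cancer lists for the father, mother and siblings also offer "I know they had cancer, but don't know what type" as option 24. It is separate both from the option for another cancer type and from the plain do-not-know option. The participant's own cancer list has a first-person version of it.

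**The concern.** Knowing that a parent or sibling has diabetes without knowing the type is an ordinary state of knowledge, and these lists cannot record it. Section 3.6 says the questionnaire exists to capture what data linkage cannot readily supply, and family history is among the topics it names. Section 5.1 links participants to NHS records, not their relatives. Whatever the form fails to record about a relative's diabetes is therefore absent from the resource unless participants are asked again.

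Diabetes also has named uses in this programme. Type II diabetes is a leading candidate for an integrated risk score (6.4), and a diabetes risk score is to decide who has HbA1c measured (2.7).

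**Working it through.** The protocol states no figure on this point, so the check sets the items against each other.

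1. **Route.** A participant who knows the mother had diabetes of unknown type correctly ticks the endocrine group at Y16D and is sent to EN_A_MOM.

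2. **Answers open to them there.**

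| Answer | What is then on record | Is diabetes recorded? |
|---|---|---|
| Type 1 or Type 2 | A stated type | Yes, but the type is a guess |
| Other, not listed | Some condition not on the list | No |
| Do not know | Endocrine or metabolic disorder, detail unknown | No |
| Prefer not to answer | Endocrine or metabolic disorder, detail refused | No |

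The father and sibling lists behave in the same way.

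3. **Recovery from other items.** The gate covers diabetes, thyroid disorder and vitamin deficiency together, so a tick there does not identify diabetes. Gestational diabetes appears in the pregnancy lists for mother and sister, and diabetic retinopathy in the eye lists. Neither covers diabetes of unknown type in general.

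4. **Instructions.** The introduction to Section 1 tells respondents to take the nearest answer when no exact one exists, which favours guessing a type. The help text at the father and mother gates tells them to tick only illnesses they are sure of. If they carry that advice into the detailed list, it favours ticking neither type. Two participants with identical knowledge can thus be recorded differently.

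5. **Comparator.** For cancer, the same section separates known disease of unknown type from not knowing at all. For diabetes it does not.

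6. **Size.** Among participants with a diabetic relative, let u be the share who do not know the type, and g the share of those who guess. Then:
 - family diabetes not recorded = u × (1 − g)
 - recorded with a guessed type = u × g

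Neither u nor g is in the documents. The unrecorded share lies somewhere between 0 and u, and no number follows.

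**The case against.** **The participant's own diabetes.** A reader might extend the point to EN_A with equal force. The documents do not support that. The medication gate (L5DF) and the diabetes drug list (DIA_MED_A), with linked primary care diagnoses and prescriptions (5.1), largely recover the participant's diabetes and its type. This part of the objection stands.

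**Appendix A as a measure of size.** A reader might turn to the row "Diabetes Mellitus – other or not specified": per million participants, 1,030 / (1,030 + 13,940 + 100) = 1,030 / 15,070 = 6.8% of incident diabetes. That does not measure the gap. The row mixes known other types with unspecified type, it comes from coded clinical records, and it assumes ages 30 to 79. It says nothing about what people know of their relatives. Among typed cases, 13,940 / (13,940 + 100) = 99.3% are Type 2, so under the same age restriction a guess of Type 2 would usually be right. Mis-typing is therefore probably the smaller harm.

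**Effect on risk scores.** A reader might infer that HbA1c selection or risk feedback would be distorted. Section 2.7 does not list the inputs of its diabetes score, and 6.4 describes candidates under consideration. Use of family history in either is plausible but not stated.

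**Lower apparent familial risk in some groups.** This too might be inferred, but it is not supported. A ticked gate followed by do-not-know can be told apart from a denial at the gate, and the protocol does not tell analysts to code it as negative. The effect is missing data. The documents show no difference between groups.

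**Testing, re-contact and other lists.** Section 3.6 describes cognitive testing, piloting and Scientific Advisory Board review. Section 3.5 allows participants to be re-contacted with further questionnaires. The thyroid entries have the same gap. The cancer items carry a source tag that EN_A lacks, so the difference may be inherited from another instrument. All of this is fair, and it limits the weight of the point. It does not supply the missing answer, and asking again later costs more than an option added now.

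**Conclusion.** The point holds for the three relatives' lists. Known diabetes of unknown type cannot be recorded truthfully. It ends up missing or with a guessed type, and no other item or linkage restores it. The conclusion rests on the printed options and on relatives not being linked, and needs no numerical assumption. The size of the loss cannot be derived from the documents. This is a modest, inexpensive improvement in data capture. It does not show that any risk score or any group comparison is wrong.

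**What to change.** Add one option to EN_A_DAD, EN_A_MOM and EN_A_SIB stating that the relative is known to have had diabetes of a type the participant does not know, modelled on option 24 of the cancer lists. Add a first-person version to EN_A for consistency, where the need is smaller.

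Give the option a code used nowhere else in the list. As printed, the unlisted-other option in these lists has code 3, the same as underactive thyroid. That may be only a numbering or extraction slip, but it should be checked at the same time.

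The cost is one answer option in four lists and one entry in the data dictionary, with no added question. The downside is that some participants who would have guessed a type will choose the new option, so analysts must define any diabetes as well as each type. The change is best made before these items are considered for the short questionnaire (3.7), which draws only on already approved questions.

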Does this chest pain go away when you stand still?

SELECT one of 4 from

- | | |
|----|----------------------|
| 1 | Yes |
| 0 | No |
| -1 | Do not know |
| -3 | Prefer not to answer |

[H10 (UKB)]

Have you ever had a screening test for bowel (colorectal) cancer?

(Please include tests for blood in the stool/faeces or a colonoscopy or a sigmoidoscopy)

SELECT one of 4 from

- | | | |
|----|----------------------|---------|
| 1 | Yes | -> H10A |
| 0 | No | |
| -1 | Do not know | |
| -3 | Prefer not to answer | |

➔ IF SEX = Female GO TO FH7 (UKB)

➔ IF SEX = (Male OR Prefer not to answer) GO TO MH2 (UKB)

Screening tests for bowel or colorectal cancer include:

- FOBT (faecal occult blood test) - this is when you are given a set of cards and asked to smear a part of your stool on three separate occasions onto the cards and then return the cards to be tested for blood.

- Sigmoidoscopy - a tube is used to examine the lower bowel. This is usually done in a doctor's office without pain relief.

- Colonoscopy - a long tube is used to examine the whole large bowel; you would usually have to drink a large amount of special liquid to prepare the bowel, and you would be given a sedative medication for the procedure.

[H10A (UKB)]

How many years ago was the most recent one of these tests?

Enter INTEGER

[Require ≥ 0 , \leq current age

Units: years]

OR

-10 Less than 1 year ago

OR

-1 Do not know

OR

-3 Prefer not to answer

→ IF SEX = Female GO TO FH7 (UKB)

→ IF SEX = (Male OR Prefer not to answer) GO TO MH2 (UKB)

If you are unsure, please provide an estimate or select 'Do not know'.

[MH2 (UKB)]

Have you ever had a blood test for prostate cancer (prostate specific antigen or PSA test)?

SELECT one of 4 from

1 Yes

0 No -> MH7 (UKB)

-1 Do not know -> MH7 (UKB)

-3 Prefer not to answer -> MH7 (UKB)

If you are unsure, select 'Do not know'.

[MH3 (UKB)]

How many years ago was your last test?

Enter INTEGER

[Require ≥ 0 , \leq current age

Units: years]

OR

-10 Less than a year ago

OR

-1 Do not know

OR

-3 Prefer not to answer

[MH7 (UKB)]

How many biological children have you had?

Enter INTEGER

[Require ≥ 0 , ≤ 200]

OR

- 1 Do not know
- OR**
- 3 Prefer not to answer

- ➔ IF ANSWER = 0 AND SEX = Male GO TO L1 (UKB)
- ➔ IF ANSWER = 0 AND SEX = Prefer not to answer GO TO FH7 (UKB)
- ➔ IF ANSWER = 1 GO TO FH3D (UKB)

[FH3C (UKB)MM]

How old were you when you had your FIRST child?

- Enter INTEGER**
[Require ≥ 8 , \leq current age
Units: years]

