- OR**
- 4 Do not remember
- OR**
- 3 Prefer not to answer

[FH3D (UKB)MM]

How old were you when you had your LAST child?

- Enter INTEGER**
[Require ≥ 8 , \leq current age
Units: years]
- OR**
- 4 Do not remember
- OR**
- 3 Prefer not to answer
-
- ➔ IF SEX = Male GO TO L1 (UKB)
 - ➔ IF SEX = Prefer not to answer GO TO FH7 (UKB)

[FH7 (UKB)]

Have you ever been for breast cancer screening (a mammogram)?

- SELECT one of 4 from**
- 1 Yes
 - 0 No -> FH8
 - 1 Do not know -> FH8
 - 3 Prefer not to answer -> FH8

[FH7A (UKB)]

How many years ago was your last screen?

Enter INTEGER

[Require ≥ 0 , \leq current age]

OR

-10 Less than 1 year ago

OR

-1 Do not know

OR

-3 Prefer not to answer

If you are unsure, please provide an estimate or select 'Do not know'.

[FH8 (UKB)]

Have you ever had a cervical smear test?

SELECT one of 4 from

1 Yes

0 No -> FH1

-1 Do not know -> FH1

-3 Prefer not to answer -> FH1

[FH8B (UKB)]

How many years ago was your last cervical smear test?

Enter INTEGER

[Require \geq current age]

OR

-10 Less than a year ago

OR

-1 Do not know

OR

-3 Prefer not to answer

If you are unsure, please provide an estimate or select 'Do not know'.

[FH1 (UKB)]

How old were you when your periods started?

Enter INTEGER

[Require ≥ 5 , \leq current age]

Units: years]

OR

-1 Do not know

OR

-3 Prefer not to answer

If you are unsure, please provide an estimate or select 'Do not know'.

[FH2 (UKB)]

Have you had your menopause (periods stopped for more than 12 months)?

SELECT one of 5 from

- | | | |
|----|-------------------------------|---------------|
| 1 | Yes | -> FH2A (UKB) |
| 0 | No | -> FH2B (UKB) |
| 2 | Not sure - had a hysterectomy | |
| 3 | Not sure - other reason | -> FH2B (UKB) |
| -3 | Prefer not to answer | |

➔ IF (ANSWER = 2 OR ANSWER = -3) AND MH7 > 0 GO TO FH5 (UKB)

➔ IF (ANSWER = 2 OR ANSWER = -3) AND MH7 < 0 GO TO FH3 (UKB)

[FH2A (UKB)]

How old were you when you had your last period?

Enter INTEGER

[Require \geq FH1 integer, \leq current age]

OR

-1 Do not know

OR

-3 Prefer not to answer

➔ IF MH7 > 0 GO TO FH5 (UKB)

➔ ELSE GO TO FH3

If you are unsure, please provide an estimate or select 'Do not know'.

[FH2B (UKB)]

How many days since your last menstrual period?

Enter INTEGER

[Require \geq 0, \leq 365,

Units: days]

OR

-10 **More than one year**

OR

-1 Do not know

OR

-3 Prefer not to answer

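### At FH2, the hysterectomy and prefer-not-to-answer codes are routed only by MH7, an item women are not asked, so these answers have no defined next question

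*Protocol*

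**What the plan says.** All items are in Protocol, Appendix E, Section 5 (Your health history).

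- After H10 and again after H10A, women are sent on by "IF SEX = Female GO TO FH7 (UKB". The other branch is "IF SEX = (Male OR Prefer not to answer) GO TO MH2 (UKB". MH7 ("How many biological children have you had") lies on that second branch only.
- FH2 offers five answers. Yes has an arrow to FH2A; No and the other not-sure answer have arrows to FH2B. Code 2, "Not sure - had a hysterectomy", and code -3 have none. They depend on two conditional lines: "IF (ANSWER = 2 OR ANSWER = -3) AND MH7 > 0 GO TO FH5 (UKB" and "IF (ANSWER = 2 OR ANSWER = -3) AND MH7 < 0 GO TO FH3 (UKB". No ELSE follows.
- The next printed item is FH2A, age at last period. Its exit, like that of FH2C, tests MH7 > 0 and otherwise goes to FH3.
- At MH7 itself, a respondent with one child follows "IF ANSWER = 1 GO TO FH3D (UKB". The last-child item on that path is labelled FH3D (UKB)MM; a second item, further on in the women's block, is labelled FH3D (UKB). Only the MM item carries "IF SEX = Male GO TO L1 (UKB" and the matching exit to FH7 for sex not stated.

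**The concern.** The two FH2 lines test a value that does not exist for the people who mainly answer FH2. A rule on MH7 > 0 or MH7 < 0 can work for someone who withheld their sex, because that person has answered MH7. It cannot work as printed for a woman, who goes from H10 or H10A directly to FH7. It also leaves out MH7 = 0, which is an ordinary answer.

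What is at stake is FH2A, the field from which age at menopause would be taken. If a woman whose periods ended at hysterectomy answers it, her age at surgery sits beside natural menopause ages under one variable name. A respondent who declined FH2 would also be asked the follow-up to the question just declined. FH2A's range check (no lower than the FH1 answer, no higher than current age) would accept a surgical age, so validation would not reveal the problem.

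**Working it through.** There is no figure of the plan's to reproduce. The check is a trace of the printed skip rules from H10 to L1.

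**Conventions used.** (a) An answer with no matching rule goes to the next printed item. The form relies on this elsewhere: Yes at FH7 has no arrow and leads to FH7A, and Yes at FH8 leads to FH8B. (b) An MH7 that was never asked is missing, hence neither above nor below zero. The form states neither convention.

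| Respondent | FH2 answer | Rule that fires at FH2 | Next items |
|---|---|---|---|
| Female | 1 (Yes) | arrow | FH2A, FH3 |
| Female | 0 or 3 | arrow | FH2B, FH2C, FH3 |
| Female | 2 or -3 | none | FH2A, FH3 |
| Sex not stated, MH7 = 2 | 2 | MH7 > 0 | FH5 |
| Sex not stated, MH7 = -3 | 2 | MH7 < 0 | FH3 |
| Sex not stated, MH7 = 0 | 2 | none | FH2A, FH3 |

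The female result is the same with 0, 1 or 2 children entered at FH3, because parity at FH3 plays no part at FH2.

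**Illustration.** A woman now 55 had a hysterectomy at 42 and answers FH2 = 2. If she is routed past FH2A, that field is blank. Under (a) and (b), FH2A = 42. She later answers FH9 = Yes and FH9A = 42. The record then holds FH2 = 2, FH2A = 42 and FH9A = 42, and the origin of the 42 can be recovered.

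**Dependence on the conventions.** If (b) is dropped and an unasked MH7 is stored as a negative code, the second FH2 rule fires and women go to FH3. The MH7 = 0 gap remains, since zero is a real answer that meets neither condition. If (a) is dropped, the next question for these codes is simply undefined.

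**After the change.** With an ELSE to FH3 for codes 2 and -3, a woman answering 2 goes FH2, FH3 (then FH3C and FH3D as parity requires), FH5, FH6, FH9, FH9A. She does not see FH2A.

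**Loss of parity data.** None. FH2A and FH2C both have the ELSE, so women's number of births is still collected at FH3.

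**The case against.** Four points can be made against the concern.

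1. The fall-through is assumed. FH2 = Yes has an explicit arrow to FH2A even though FH2A is the next item, so FH2 may not rely on next-item flow. This stands as a limit on the consequence. It does not supply a route for codes 2 and -3.
2. Non-answers on this form have negative codes (-1, -3, -10). If an unasked item were stored the same way, women would reach FH3. This is possible, but those are codes that a respondent selects, and nothing says that a skipped item receives one.
3. FH2A asks about the last period, so an age at surgery is a true answer to it, and FH2 with FH9/FH9A identifies the record. A respondent who declined FH2 can decline FH2A too. This stands and makes the harm modest.
4. A builder would probably see what was meant, because FH2A and FH2C show it. That argues for an easy fix, not for leaving the rule as it is.

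Two stronger readings are tempting and are not supported. First, a reader might infer from the MH7 = 1 target that men with one child are sent to the women's FH3D and on through contraception, HRT, hysterectomy and ovary items, and that people with one child and sex not stated lose the screening and menopause items permanently. GO TO targets in this appendix routinely drop the block suffix. The father's section points to AUTO_A and ANX_B where the items are AUTO_A_DAD and ANX_B_DAD, although items labelled exactly AUTO_A and ANX_B exist in the respondent's own section. On that usage, FH3D (UKB) can mean the adjacent MM item, whose exits are correct. The label is ambiguous; misrouting is not established. Permanent loss would not follow either, since re-contact for further questionnaires (Section 3.5) and NHS record linkage (Section 5.1) are planned.

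Second, a reader might apply the FH2 gap to all women in Table 1. The two rules concern only answers 2 and -3, and no document gives the share who would choose them.

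**Conclusion.** The FH2 routing is faulty as printed. Codes 2 and -3 depend on an item not asked when SEX = Female, and MH7 = 0 is left out in any case. That part needs no assumption beyond treating an unasked item as having no value, and the MH7 = 0 gap does not need even that.

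The mixing of surgical with natural ages in FH2A is conditional on next-item flow and on an unasked MH7 not being stored as negative. Where it occurs it is recoverable through FH2 = 2 and FH9/FH9A, provided the analyst knows to look. Its size cannot be given in numbers from the documents. This is a small, real defect in the instrument, worth correcting because the correction is so cheap. The MH7 = 1 target is a labelling ambiguity and no more.

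**What to change.** At FH2, keep the first rule and replace the second, so that for answers 2 and -3 the routing is: MH7 > 0 to FH5, ELSE to FH3. The ELSE must apply to those two answers only, so that the arrows for 0, 1 and 3 are untouched. This covers women and MH7 = 0, and matches FH2A and FH2C.

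Separately, as a clarification, change the MH7 = 1 target from FH3D (UKB) to FH3D (UKB)MM.

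The cost is two lines of routing text. No item is added. If data have already been collected with this routing, the data dictionary should tell users to read FH2A together with FH2 and FH9/FH9A.
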